7.2.2 Demographic and Other Baseline Characteristics

7.2.2.1 Demographics

[Analysis Set: FAS, SAF, PDAS]

The following demographic variables will be summarized.

Demographic Variables

Item	Classification	
Age (years) at Week 0	Measurement value	
	<65,>=65	
Sex	Male, Female	
Body Weight (kg) at Week 0	Measurement value	
	<- 40 kg,	
	40 kg <- 60 kg,	
	60 kg <- 80 kg,	
	> 80 kg	
Complications at Week 0	No, Yes	
Concomitant Medications at Week 0	No, Yes	
Concomitant DMARD at Week 0	No, Yes	
Concomitant MTX at Week 0	No, Yes	
Concomitant DMARD category at Week 0	MTX, DMARD except for MTX only,	
	None	
Concomitant Steroid at Week 0	No, Yes	
Prednisone dose (mg/day) at Week 0	Measurement value	
	None, $0 = < 5 \text{ mg/day}, > 5 \text{ mg/day}$	
Study Region	Japan, Korea, Taiwan	

7.2.2.2 Baseline Disease Activity

[Analysis Set: FAS, SAF, PDAS]

The following baseline disease activity variables will be summarized by descriptive statistics. The summaries will be presented for values at both "Week 0" and "baseline of preceding study".

- o TJC-68
- o TJC-28
- o SJC-66
- o SJC-28
- o SGAP (100 mm VAS)
- SGA (100 mm VAS)
- PGA (100 mm VAS)
- HAQ-DI (scale 0 3)
- o CRP (mg/dL)
- o ESR (mm/hr)
- o DAS28-CRP
- o DAS28-ESR
- o SDAI score
- CDAI score
- WPAI (only for subjects who transferred from studies RAJ3 or RAJ4)
- SF-36V2®

In addition, following baseline efficacy categorical variables will be summarized as well.

- \circ Baseline CRP (< 1.0, >= 1.0)
- Baseline DAS28-CRP/ ESR (<= 3.2, 3.2<-5.1, > 5.1)

7.2.2.3 RA History

[Analysis Set: SAF]

The following RA history variables will be summarized. The summaries will be presented for values at both "Week 0" and "baseline of preceding study", unless specifically stated otherwise.

RA History and Analysis Methods

Item	Classification	
ACR 1991 Revised Criteria for Global Functional	Class I, Class II, Class IV	
Status in RA		
Steinbrocker Classification	Stage I, Stage II, Stage IV	
Duration of RA (years) #	Measurement value	
	< 5 years, >- 5 years	
	< 1 year,	
	< 1 year, 1 year -<5 years,	

		5 years -< 10 years, >- 10 years	
Prior MTX # Use		Non-User, User	
	ximum Dose (mg/week)	,	
	ctivity	Response, Inadequate Response,	
	•	Unknown	
Tole	erance	Intolerance, Tolerance, Unknown	
MTX Dose (mg/week) at Week 0		Measurement value	
		None,	
		$0 \le 8$ mg/week,	
		8 <- 12 mg/week,	
		> 12 mg/week	
Prior Non-Biologic DMAR	D Use	Non-User, User	
Except for MTX #			
Prior Anti-TNF DMARD U	Jse Use	Non-User, User	
Prior Biologic DMARD #	Use	Non-User, User	
	Reactivity	Response, Inadequate Response,	
		Unknown	
Prior Biologic DMARD-IR #		No, Yes	
Number of Prior Biologic I	OMARDs #	0, 1, 2, >= 3	
Number of Prior DMARDs (including biologics) #		0, 1, 2, >= 3	

^{#:} only for baseline of preceding study

7.2.2.4 Medical Condition

[Analysis Set: SAF]

Medical Conditions at "baseline of preceding study" will be coded using MedDRA (Version 11.1) and summarized.

7.2.3 Concomitant Medications

[Analysis Set: SAF]

Previous DMARD medications up to Screening of preceding study will be summarized as described in 7.2.2.3.

For subjects who shift from RAJ3/4, concomitant medications (Non-Biologic DMARD/ Medications except for Non-Biologic DMARD) will be coded using WHODDE (B2) (V2011SEP) and summarized with preferred WHO name, respectively from following CRF page. Concomitant medications are defined as any drug medications after the first dose of study drug at RAJ2 up to the end of study.

- Concomitant Medication 2B -page of the CRF
- Concomitant Medication (Non-Biologic DMARD) -page of the CRF

Subjects taking the same medication multiple times will be counted once per medication.

In addition to this, the maximum/ minimum MTX Dose (mg/week) during the study period will be summarized by descriptive statistics.

7.3 Study Drugs

These analyses will be also conducted for overall by Study Region.

7.3.1 Exposure

[Analysis Set: SAF]

Duration of exposure during RAJ2 will be summarized in two ways.

- Descriptive statistics will be presented
- Exposure time for overall period will be categorized according to the following categories:
 - \circ 0 1 month
 - \circ 1 <- 3 months
 - \circ 3 <- 6 months
 - 6 <- 12 months
 - 12 <- 24 months
 - o 24 <- 36 months
 - 36 <- 48 months
 - 48 <- 60 months
 - o 60 <- 72 months
 - 72 <- 84 months
 - o 84 months <

Counts and percentages of subjects in each category will be summarized.

In addition to this, the following information on drug exposure will be presented:

- Number and percent of subject with dose increase/ dose decrease/ drug suspension/ drug interruption
- Number of experience for dose increase/ dose decrease/ drug suspension/ drug interruption per subject
- Duration from First Study Drug Taken up to First Dose Change to ASP015K 100 mg (from RAJ1) or 150 mg (from RAJ3/RAJ4)
- Maximum Dose of Study Drug (ASP015K 50 mg/ 100 mg/ 150 mg)

The following Kaplan-Meier plot of time-to-event from initial dose will be constructed.

		Event	Censor
Time to changing initial 50mg	RAJ1	Dose increase Discontinuation	Study Completion
Time to changing initial 100mg	RAJ3/4	Dose increase Dose decrease Discontinuation	Study Completion
Time to dose increasing initial 100mg	RAJ3/4	Dose increase	Study Completion Discontinuation Dose decrease
Time to dose decrease initial 100mg	RAJ3/4	Dose decrease	Study Completion Discontinuation Dose increase

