### 3.4 Discontinuation Criteria for Individual Subjects

A discontinuation means that a subject who has enrolled in the study prematurely terminates study treatment prior to the completion of all protocol-required elements.

The subject is free to withdraw from the study treatment and/or study for any reason and at any time without giving reason for doing so and without penalty or prejudice. The investigator is also free to terminate a subject's involvement in the study at any time if this is considered necessary because of the subject's clinical condition.

Discontinuation Criteria for Individual Subjects:

The investigator/sub-investigator should discontinue the study if any of the following criteria are met:

1. Subject withdraws consent.
2. The study drug is not sufficiently effective, and a change in treatment method is deemed to be in the subject's best interest by the investigator or sub-investigator.
3. Symptomatic CPK elevation, defined as  $CPK > 1.5 \times ULN$  with severe unusual myalgia, muscular weakness, or muscle twitching\*.  
\* Muscle twitching: A condition in which there is a cramp in a muscle, such as cramps in the calves
4. Any event of myopathy defined as severe unusual myalgia, muscular weakness, and muscle twitching\* regardless of CPK level that persists for at least 2 weeks or that worsens rapidly within 2 weeks.  
\* Muscle twitching: A condition in which there is a cramp in a muscle, such as cramps in the calves
5. Subject infected with HBV who has tested positive for either of or both of HBc and HBs antibodies and is found to be positive for HBV-DNA assay during the study period. Abrupt discontinuance of immunosuppressive therapy may precipitate severe or fulminant hepatitis. Therefore, when HBV reactivates, nucleic acid analog therapy should be immediately initiated, and a hepatologist should be consulted regarding the continuation of ASP015K and concomitant DMARD (unique to Japan: as indicated by "Proposal for Management of Rheumatic Disease Patients with Hepatitis B Virus Infection Receiving Immunosuppressive Therapy" by the Japan College of Rheumatology).

- CONFIDENTIAL -

6. Subject has a malignant tumor.
7. Subject has an adverse event (AE) such as a serious infection, and the investigator or sub-investigator considers that it is not in the subject's best interest to continue the study.

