#### **5.1.2 Increase or Reduction in Dose of the Study Drugs**

The dose increase/reduction of study drugs is allowed only when the following criteria are met. For subjects who have been receiving ASP015K at a dose of 50 mg/day in Japan, the dose will be increased to 100 mg/day after approval in Japan. Any subjects for whom the dose cannot be increased should be withdrawn from the study.

[The increase in dose from 50 mg/day to 100 mg/day]

- CONFIDENTIAL -

Japan: For subjects who have been receiving ASP015K at a dose of 50 mg/day in Japan, the dose will be increased to 100 mg/day after approval. Any subjects for whom the dose cannot be increased should be withdrawn from the study.

Korea and Taiwan: When the investigator or sub-investigator judges that there is no safety problem in the subject, the dose may be increased from 50 mg to 100 mg.

[The increase in dose from 100 mg/day to 150 mg/day]

The dose may be increased from 100 mg to 150 mg at the time point when the following 2 conditions are met:

- 1) The subject has taken ASP015K 100 mg for at least 4 weeks, and the DAS28-ESR score is 3.2 or higher (moderate disease activity or high disease activity) on the study visit days.
- 2) When the investigator or sub-investigator judges there to be no problem with safety for the subject in the assessment performed on the study visit day on which the DAS28-ESR score of 3.2 or higher was exhibited.

[The reduction in dose from 100/day mg or 150 mg/day to 50 mg/day]

Japan: After the NDA approval in Japan, dose reduction for the study drugs is not allowed.

Korea and Taiwan: After the dose increase, the dose may be reduced from 100 mg/day or 150 mg/day to 50 mg/day at the discretion of the investigator or sub-investigator.

The investigator or sub-investigator will decide whether or not to reduce the dosage on the basis of the following criterion.

- If an AE with NCI-CTCAE grade classification of Grade 2 or higher has developed.

A dose increase after a dose reduction and a dose reduction after a dose increase are allowed according to the above criteria.

If the dose of study drug has been increased or reduced, the investigator or sub-investigator should record this information in the CRF.

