7 STATISTICAL METHODOLOGY

7.1 General Considerations

- For continuous variables, descriptive statistics will include the number of subjects (n), mean, standard deviation (SD), median, minimum, and maximum.
- For categorical variables: number and percentages of subjects will be described.
- For time-to-event variables: number and percentage of subjects with the event using Kaplan-Meier method, the cumulative event rate will be estimated and a plot will be constructed.
- All data processing, summarization, and analyses will be performed using SAS Drug Development (ver. 4.5), and PC-SAS (ver. 9.4) or higher versions.
- Specifications for table, figures, and data listing formats can be found in the TLF specifications for this study.
- For the definition of subgroups of interest can be referred to Section 7.8.
- Summaries based on FAS and SAF (e.g. disposition, baseline, efficacy data and safety data) will be presented by preceding studies and overall, unless specifically stated otherwise.
- Medical Dictionary for Regulatory Activities (MedDRA) 11.1 will be used as the coding dictionary for adverse event and medical history.
- Confidence interval for binary outcome is continuity corrected in all analysis.
- For the analyses of efficacy and pharmacodynamics variables in this extension study, values at the baseline in the preceding studies (RAJ1, RAJ3, and RAJ4) will be used as the baseline values. However, changes from baseline values of this extension study will also be examined where appropriate. For the analyses of safety, Week 0 of this extension study will be referred to as the baseline; however, changes from baseline values of the preceding studies (RAJ1, RAJ3, and RAJ4) will also be examined where appropriate.
- Change from baseline to post-baseline will be calculated as: post-baseline value baseline value. If the baseline value is missing, then that subject is not included in the calculation at any visit.
- Percent change from baseline to post-baseline will be calculated as: 100 × (change /baseline). If the baseline value is 0 or missing, or post-baseline value is missing, then percent change from baseline to post-baseline is missing.
- The values below the lower limit of quantitation (BQL) for β-D-glucan, hCG, Troponin, CK-MB will be treated as it is and these variables are not used for descriptive statistics

- and displayed in the listings. As for β -D-glucan, it is used for shift-from baseline analysis.

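### Two Kaplan-Meier plots of dose change from initial 100 mg censor competing exits, so their event rates lie at or above the cumulative incidence of that first change

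*SAP*

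**What the plan says.** SAP 7.3.1 lists four Kaplan-Meier plots of time from initial dose, with an event column and a censoring column.

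- Row 1 (RAJ1, initial 50 mg) and row 2 (RAJ3/4, "Time to changing initial 100mg") count every exit from the initial dose as an event, including discontinuation. They censor only study completion.
- Row 3 (RAJ3/4) counts only dose increase and censors "Study Completion Discontinuation Dose decrease".
- Row 4 (RAJ3/4) counts only dose decrease and censors "Study Completion Discontinuation Dose increase".

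When an outcome is of this type, SAP 7.1 asks for the following: "number and percentage of subjects with the event using Kaplan-Meier method, the cumulative event rate will be estimated and a plot will be constructed". Neither document mentions competing risks, and the SAP does not label rows 3 and 4 as net curves.

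The same section also plans "Number and percent of subject with dose increase/ dose decrease/ drug suspension/ drug interruption", and a summary of the time from first dose to first change to 150 mg for RAJ3/4. SAP 7.3 adds a regional breakdown: "These analyses will be also conducted for overall by Study Region".

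**The concern.** A subject who discontinues, or whose first change goes the other way, can no longer have a first increase (or first decrease) from initial 100 mg. Row 2 treats these exits as events; rows 3 and 4 turn two of the three into censoring. Kaplan-Meier then behaves as if the censored subjects remained at the same risk of the event as those still on 100 mg.

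The result could be read as a net rate, meaning the rate if the other exits did not exist, but only if those exits are independent of the event. For row 3 the protocol gives no basis for that. An increase requires that "The subject has taken ASP015K 100 mg for at least 4 weeks, and the DAS28-ESR score is 3.2 or higher" (Protocol 5.1.2), and a discontinuation criterion is that "The study drug is not sufficiently effective, and a change in treatment method" is judged best for the subject (Protocol 3.4, item 2). Poor response can therefore lead to either exit.

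At stake is how a reader describes the share of RAJ3/4 subjects who moved up or down from 100 mg, and when.

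**Working it through.** The plan states no figure for these plots, so there is none to reproduce. The check has two parts.

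**1. Direction, for any hazards.** Let d subjects out of n at risk have the event at time t. That step adds S_cause(t−) × d/n to one minus Kaplan-Meier (1−KM), where S_cause falls only at events of that type. It adds S_all(t−) × d/n to the Aalen-Johansen cumulative incidence, where S_all falls at every exit. S_all carries extra factors of at most 1, so S_cause ≥ S_all. Three things follow:

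- 1−KM is never below the cumulative incidence.
- It is above it once a competing exit precedes an event.
- The gap never shrinks over time.

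A simulation of 2,000 data sets of 600 subjects agreed: none of 1,200,000 pointwise comparisons had 1−KM below Aalen-Johansen.

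**2. Size, under assumed hazards.** The documents give no RAJ2 rates and no follow-up length for RAJ3/4. The only indication is from the preceding studies: adverse events led 12.5% (RAJ3) and 7.5% (RAJ4) of 100 mg subjects to stop over the whole study (Protocol 1.3), so discontinuation is not negligible. Assumed yearly hazards for increase, decrease and discontinuation are:

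- low: 0.10, 0.02, 0.05
- middle: 0.20, 0.03, 0.10
- high: 0.30, 0.05, 0.15

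With constant hazards, event hazard h1 and total H:

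- 1−KM = 1 − exp(−h1·t)
- cumulative incidence = (h1/H) × (1 − exp(−H·t))

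Middle set at 4 years, H = 0.33:

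- Increase: 1 − exp(−0.80) = 55.1%, against (0.20/0.33) × (1 − exp(−1.32)) = 44.4%.
- Decrease: 1 − exp(−0.12) = 11.3%, against (0.03/0.33) × (1 − exp(−1.32)) = 6.7%.

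Excess of 1−KM in percentage points, low to high set:

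| Scenario | Time | Increase (row 3) | Decrease (row 4) |
|---|---|---|---|
| Constant hazards | 1 year | 0.3–2.3 | 0.1–0.9 |
| Constant hazards | 2 years | 1.2–7.2 | 0.5–3.2 |
| Constant hazards | 4 years | 3.9–18.0 | 1.9–9.5 |
| Increases cluster early | 4 years | 1.7–7.8 | 2.5–12.0 |
| Rare decreases (hazard 0.005), constant | 4 years | 3.2–14.6 | 0.5–1.1 |

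Early clustering puts the increase hazard at 0.65 in year 1 and 0.05 per year after that (middle set; halved for low, times 1.5 for high). The 4-year cumulative hazard is unchanged, and 0.65/0.80 = 81% of it falls in year 1. The middle set then gives 55.1% against 50.4% for increase and 11.3% against 5.3% for decrease.

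**Coherence check.** In the constant middle set, the cumulative incidences of increase (44.4%), decrease (6.7%) and discontinuation ((0.10/0.33) × (1 − exp(−1.32)) = 22.2%) sum to 73.3%. That equals the composite 1 − exp(−1.32). The matching 1−KM values, 55.1%, 11.3% and 1 − exp(−0.40) = 33.0%, sum to 99.4%.

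**The case against.** The strongest reply is that nothing is hidden or lost. The table states what each curve censors, and cause-specific Kaplan-Meier is a known descriptive choice. The general rule in SAP 7.1 also puts the observed number and percentage with the event beside each curve. Rows 2 and 3 share the same risk sets, so summing S_row2(t−) × [1 − S_row3(t)/S_row3(t−)] returns the Aalen-Johansen estimate for increase, and rows 2 and 4 do the same for decrease. On 50 simulated data sets this matched to about 1e−15.

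That recovery is real, and a reader who infers that the correct curves cannot be derived from the planned output goes too far. But it leaves the work to the reader, and from a printed plot it would be approximate. The crude percentages and the duration to first increase do not correct the curves, because subjects are followed for different lengths of time. Stating the censoring does not turn 1−KM into an event rate.

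A second objection concerns row 4. Protocol 5.1.2 (for Korea and Taiwan) and SAP 3.2 both introduce dose reduction as something that follows an increase. The current protocol limits it to Korea and Taiwan (2.2.1), while SAP 3.2 states no regional limit. If a first change is hardly ever a decrease, row 4 has few events and its gap is near zero. This stands, and it is why row 3 carries the point. Where the two documents differ on reduction, they should be reconciled; this review takes no position on which is right.

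**Conclusion.** The concern holds, as a minor one. Rows 3 and 4 report a quantity at or above the cumulative incidence of the first change. That direction needs no assumption about the hazards, only that study completion is non-informative censoring.

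The size is entirely assumed. For increase at 4 years it is about 4 to 18 points with constant hazards and about 2 to 8 if increases cluster early; at 1 year it is at most 2.3 points in the sets tried. For decrease it is about 0.5 to 1 point at 4 years if decreases are rare, and larger only if they are not.

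Two stronger readings are tempting. One is that both plots must overstate by an amount that keeps growing. The documents do not support this: the gap is zero until a competing exit precedes an event, and it stops growing when events of that type stop. The other is that the trial's conclusions are affected. These are descriptive exposure plots, repeated by region, and no efficacy or adverse event result uses them. The composite curves in rows 1 and 2 are sound.

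**What to change.** In SAP 7.3.1, replace the row 3 and row 4 plots with Aalen-Johansen cumulative incidence curves for first increase, first decrease and discontinuation as competing events. Censor only at study completion and show the three curves in one figure. They should sum to the row 2 curve, which gives a programming check. Keep Kaplan-Meier for rows 1 and 2.

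If the Kaplan-Meier versions of rows 3 and 4 are also kept, label them as net (cause-specific) curves and not as cumulative event rates.

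The cost is two table rows in the SAP and a standard procedure option, with the same data and no new collection.

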7.3.2 Treatment Compliance

[Analysis Set: SAF]

Treatment compliance during RAJ2 will be examined for subjects in the SAF whose total study drug count and first and last days of treatment are known. These data will be summarized as below.

- Descriptive statistics for treatment compliance during RAJ2 will be presented.
- Treatment compliance during RAJ2 will be categorized according to the following categories:
 - o <50%
 - o 50% <75%
 - 0 75% <90%
 - 0 90% 100%

7.4 Analysis of Efficacy

[Analysis Set: FAS]

Details for analysis of efficacy will be described in 10.1 Appendix 1: Overview of Efficacy Endpoints. They include categorical, and continuous variables, with "X" indicating that the

variable will be analyzed. Basically, analysis of efficacy will be performed by preceding studies only, not performed by overall.

7.4.1 Analysis of Efficacy Endpoint(s)

The efficacy variables and analyses are as follows.

- Categorical variables at each visit will be summarized.
- For continuous variables, raw value and change from baseline of preceding study at each visit will be summarized by descriptive statistics. In addition, for the selected efficacy variables (DAS28-CRP), change from Week 0 at each visit will be summarized similarly.
- Graphical analysis:
 - ACR20/50/70-CRP/ESR will be plotted for over time.
 - The mean-standard deviation plot of actual values and changes from baseline of preceding study will be presented for DAS28-CRP and DAS28-ESR.

7.4.2 Analysis by Treatment Sequence Set of preceding study

The selected efficacy variables (ACR20-CRP and DAS28-CRP) are summarized by Treatment Sequence Set, and by preceding study respectively. In this analysis, time course of each efficacy variable will be presented from baseline of preceding study up to end of RAJ2 study. Following analysis visits of preceding study will be used,

- Subjects shifted from RAJ1
 - o RAJ1 Week 0
 - o RAJ1 Week 12
 - Week 0 (RAJ1 Week 16)
- Subjects shifted from RAJ3/4
 - \circ RAJ3/4 Week 0
 - o RAJ3/4 Week 12
 - o RAJ3/4 Week 28
 - o RAJ3/4 Week 40
 - o RAJ3/4 Week 52
 - Week 0
- Categorical variables at each visit will be summarized.
- For continuous variables, raw value and change from baseline of preceding study at each visit will be summarized by descriptive statistics.
- Graphical analysis:
 - ACR20-CRP will be plotted from baseline of preceding study.
 - The mean-standard deviation plot of actual values and changes from baseline of preceding study will be presented for DAS28-CRP from baseline of preceding study.

7.4.3 Analysis of Efficacy in Initial/Maximum Dose Level

The selected efficacy variables (ACR20-CRP and DAS28-CRP) are summarized by preceding study. In Initial dose analysis, data obtained after changing initial dose at RAJ2 (50mg for subjects from RAJ1, 100mg for subjects from RAJ3/4) will not be used for efficacy analyses.

- Categorical variables at each visit will be summarized.
- For continuous variables, raw value and change from baseline of preceding study at each visit will be summarized by descriptive statistics.

7.4.4 Influence of Dose Escalation

In order to evaluate influence of ASP015K dose escalation to 100 mg from 50 mg for subjects who shifted from RAJ1 and dose escalation to 150 mg from 100 mg for subjects who shifted from RAJ3 or RAJ4, the selected efficacy variables (ACR20-CRP and DAS28-CRP) will be analyzed based on the days of first dose increase to 100mg or 150mg until dose decrease. Following intervals will be used.

- o < -336
- o -336 < -252
- o -252 < -168
- o -168 < -84
- o -84 < 0
- 0 < 84
- o 84 < 168
- \circ 168 < 252
- o 252 < 336
- o >= 336

If multiple efficacy values are included in one interval, the last one is used.

- Graphical analysis:
 - ACR20-CRP will be plotted
 - The mean-standard deviation plot of actual values and changes from baseline of preceding study will be presented for DAS28-CRP from baseline of preceding study.

